## SHORT TITLE:

permanently and inform study staff of this decision

- [name] will submit the serious adverse event to the Institutional Review Board at the Children's Mercy Hospital within 7 days of learning of the event and will work with the IRB to determine the need for changes to study procedures and the study protocol
- [name] will provide a completed copy of the FDA "MED WATCH" form to the Data Safety and Monitoring Board within 7 days of learning of the event
- [name] will submit the serious adverse event to the NIDA program officer within 7 days of learning of the event
- A copy of the completed "MED WATCH" form will be kept in the study file

## 27.0 Data Analysis\*

### 27.1

Measures: *Participant demographics and clinical characteristics* (e.g., age of initiation, nicotine dependence) will be assessed at baseline. The outcome measures, method of assessment, relevant stakeholders and detailed description are depicted in Table 3 and sample survey items in Table 4. *Preliminary efficacy* will be assessed via self-reported

Table 3: Assessment of Proctor Outcome Measures				
Outcome Measure	Definition	How/What Assessed	Team member/ Stakeholder(s)	Description
Preliminary Efficacy	Impact on treatment outcomes of the intervention vs. control	Survey	AYA participant	Self-reported and biochemically verified (salivary cotinine) 30-day tobacco/ENDS use abstinence at 3-mo follow up survey (primary outcome) Self-reported motivation & confidence immediately after intervention and at 3-mo follow up survey
Acceptability	Participant satisfaction with the intervention components	Survey Study process data	AYA participant, Parent/Guardian AYA participant	Likert-scale AYA and parent/guardian survey items on intervention satisfaction after the session (AYAs and parent/guardians) and at 3-mo survey (AYAs only)* Proportion of eligible patients who enroll, complete the intervention & booster sessions
Feasibility	Intervention fit within the context; suitability for everyday use; practicality	Field notes, session length, & survey items	Health Educator, [name] score of Likert-scale items on intervention feasibility (immediately post intervention*; Session duration (minutes) from audio-recordings; Health educator field notes of interruptions to workflow and modifications to care
Fidelity	Extent to which the intervention is delivered as intended?	Audio-recordings of Health Educator and [name] sessions	Health Educator, [name]. [name] and [name] will review audio-recordings and perform fidelity scoring of intervention sessions utilizing adapted fidelity rating scales

\*For outcomes assessed by 5-point Likert-scale survey items, we will calculate mean scores of survey items by categories (e.g., mean AYA satisfaction/acceptability for each intervention component and for the overall intervention). Mean scores  $\geq 4$  will be considered satisfactory.

30-day point prevalence tobacco/ENDS abstinence using the timeline follow-back method at 3-month follow-up. To obtain a biochemically verified outcome and to encourage accurate self-reporting we will assess salivary cotinine from all participants (not currently on NRT) who report abstinence. We will assess this by either mailing a saliva specimen home collection kit to then be return mailed (pre addressed and paid)

## SHORT TITLE:

to our study team or we will also offer the option of completing a home saliva cotinine test which do not require return mailing. For this option home saliva cotinine tests will be mailed to the participant. The study team will then schedule a secure Microsoft Teams video call to witness saliva test completion and results or photos of the test results can be emailed at a convenient time to [[contact]](mailto:[contact]), a secure email address created specifically for this research study. Although accurate verification will not be possible with participants who are occasional users or those on NRT, this will also allow us to evaluate the feasibility of collecting saliva by mail or completing secure video or photos witnessed home saliva cotinine tests in this population which will be informative for future studies with daily ENDS users. Secondary efficacy outcomes will include self-reported motivation and confidence to quit immediately post-intervention and at 3-month follow up. We will assess *acceptability* with the overall intervention and intervention components via survey immediately post intervention (AYAs and parents) and at 3 month follow-up (AYAs). Acceptability will also be evaluated via participant enrollment and session completion rates. *Feasibility* will be assessed via intervention duration in minutes from audio recordings and [name] and the health educator will complete a brief survey and record field notes to assess feasibility (e.g., impact on workflow, disruption, suitability). To assess *fidelity* we will review audio recordings and rate health educator intervention and control sessions based on a previously developed fidelity rating scales To assess *preliminary efficacy*, differences in self-reported and biochemically verified 30-day tobacco/ENDS use abstinence at 3-month follow up (primary outcome) will be analyzed using a generalized linear model assuming an underlying binomial distribution and logit link function to compare between study arms. Motivation and Confidence to quit will be analyzed using a repeated measures analysis of variance. Potential differential outcomes based on sex and demographic factors will be explored. Chi-square (categorical variables) and Wilcoxon Rank Sum (continuous variables) tests will be used to assess participation bias. For acceptability, we will calculate the proportion of AYA participants and parents/guardians in the intervention arm with mean ratings of satisfaction and acceptability of  4 on the 5-point Likert scale. In addition, frequencies and percentages will be used to describe the enrollment and session completion rate. For *feasibility* we will conduct thematic analysis of field notes and conduct simple descriptive analyses (means, frequencies, percentages) of the brief survey items completed by [name] and the health educator and session length data. *Fidelity* will be summarized utilizing similar descriptive analyses of the fidelity ratings (e.g., percentage of intervention steps completed; mean rating of key MI skill adherence).

CYP2A6 genotype-predicted phenotype (slow, intermediate, extensive) and other genetic variants of interest may be explored as co-variants in the analysis. Given the exploratory nature of the genetic analysis, we are likely underpowered to find significant association across numerous genetic co-variants, but these data may inform future studies designed to evaluate the relationship.

SHORT TITLE:

**27.2** Our proposed sample size [n=144 (96 treatment, 48 control)] is well within the recommendations for behavioral intervention development pilot trials based on what is feasible to recruit in our hospital and judged to be sufficient to evaluate efficacy (i.e., self-reported/biochemically verified abstinence) in a preliminary behavioral design trial. With respect to percentage reporting self-reported and/or biochemically confirmed abstinence at 3-mo follow up the margin of error (ME) around our observed outcomes depends on the observed proportion with the largest ME occurring when the proportion is 50%. Our sample size is sufficient to provide a ME of 10% (if the proportion is 50%) or less.

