## **2.2 Hypothesis to be tested/Exploratory study design:**

We hypothesize the intervention arm will have higher rates of biochemically confirmed self-reported tobacco use abstinence (preliminary efficacy; primary outcome) compared to the control arm at 3 month follow up.

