## SUBJECT MANAGEMENT

### 6.0 Inclusion and Exclusion Criteria\*

#### 6.1 Eligibility Criteria:

AYA patients	Inclusion: 14-21 years, current or past 30-day ENDS use, hospitalized, English speaking  Exclusion: severe illness, severe psychiatric illness or cognitive impairment
Parents/Guardians	Inclusion: AYA agrees to parent/guardian surveys

Hospital Staff	Inclusion: Staff of enrolled AYA agrees to participate
----------------	--

**6.2 Equitable Selection:** There are no exclusions based on sex or race/ethnicity. We will plan to enroll a balanced study sample by reviewing the EHR and approaching a study population that is representative of the hospitalized AYAs at our hospital. As a majority of patients are English speaking we will plan to enroll English speaking participants, we will provide a parent information sheet in Spanish for participants whose parents speak Spanish but the enrolled participant must be English speaking.

**6.3 Vulnerable Populations:** *Check any vulnerable populations that are being targeted for enrollment into the study: (Members of the following populations may not be included as participants in the research unless selected here.)*

- Children/Minors (under 7 years of age)
- Children/Minors (7-17 years of age)
- Neonates (infants less than 30 days old)
- Neonates of Uncertain Viability (infants less than 30 days old)
- Non-Viable Neonates (infants less than 30 days old)
- Wards of the State
- Fetuses
- Pregnant Women
- Adults with impaired decision-making capacity
- CM Employees
- CM Students/Residents/ Fellows
- Economically or Educationally Disadvantaged Persons
- Prisoners

Adolescents aged 14-17 years:

Adolescent assent procedures will follow practices accepted by the Society for Adolescent Health and Medicine and current regulatory guidelines and align with those previously used for CM studies involving adolescents

All adolescents will be encouraged to ask questions, provided necessary time to consider participation, and able to stop participation at any time, should they choose to do so.

All adolescents will be assured that their decision to participate or not will have no impact on their relationship with and care received at CM.

Wards of the State:

Another population that requires close attention are those who are wards of the state. This population is extremely important to capture, as they are known to have higher risk

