Parents/guardians of AYAs will be asked to complete a post-intervention survey. The health educator will complete brief survey items and field notes after each session. The AYA intervention and control sessions will be audio-recorded and reviewed by Drs. [name] and [name] to assess fidelity and provide feedback. [name] will review audio-recordings of [name] sessions (e.g., Assist: NRT prescription) to assess fidelity and give feedback.

Participant demographics and clinical characteristics (e.g., age of initiation, nicotine dependence) will be assessed at baseline. The outcome measures, method of assessment, relevant stakeholders and detailed description are depicted in Table 3 and sample survey items in Table 4. *Preliminary efficacy* will be assessed via self-reported 30-day point prevalence tobacco/ENDS abstinence using the timeline follow-back method at 3-month follow-up.⁷³ To obtain a biochemically verified outcome and to encourage accurate self-reporting we will assess salivary cotinine via mailed samples from all participants (not currently on NRT) who report abstinence. Although accurate verification will not be possible with participants who are occasional users or using NRT, this will also allow us to evaluate the feasibility of collecting saliva by mail in this population which will be informative for future studies with daily ENDS users. Secondary efficacy outcomes will include *self-reported motivation and confidence to quit immediately post-intervention and at 3-month follow up*.^{65, 74,75} We will assess *acceptability* with the overall intervention and intervention components via *survey* immediately post intervention (AYAs and parents) and at 3 month follow-up (AYAs). Acceptability will also be evaluated via participant *enrollment and session completion rates*. *Feasibility* will be assessed via *intervention duration* in minutes from audio recordings and [name] and the health educator will complete a brief survey and record field notes to assess feasibility (e.g., *impact on workflow, disruption, suitability*). To assess *fidelity* we will *review audio recordings* and rate health educator intervention and control sessions based on a previously developed fidelity rating scales.

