To assess *preliminary efficacy*, differences in self-reported and biochemically verified 30-day tobacco/ENDS use abstinence at 3-month follow up (primary outcome) will be analyzed using a generalized linear model assuming an underlying binomial distribution and logit link function to compare between study arms. Motivation and Confidence to quit will be analyzed using a repeated measures analysis of variance. Potential differential outcomes based on sex and demographic factors will be explored. Chi-square (categorical variables) and Wilcoxon Rank Sum (continuous variables) tests will be used to assess participation bias. For acceptability, we will calculate the proportion of AYA participants and parents/guardians in the intervention arm with mean ratings of satisfaction and acceptability of ≥ 4 on the 5-point Likert scale. In addition, frequencies and percentages will be used to describe the enrollment and session completion rate. For *feasibility* we will conduct thematic analysis of field notes and conduct simple descriptive analyses (means, frequencies, percentages) of the brief survey items completed by [name] and the health educator and session length data. *Fidelity* will be summarized utilizing similar descriptive analyses of the fidelity ratings (e.g., percentage of intervention steps completed; mean rating of key MI skill adherence). Potential differential outcomes based on sex and demographic factors will be explored. Chi-square (categorical variables) and Wilcoxon Rank Sum (continuous variables) tests will be used to assess participation bias.

Sample Size Our proposed *sample size* [$n=144$ (96 treatment, 48 control)] is well within the recommendations for behavioral intervention development pilot trials based on what is feasible to recruit in our hospital and judged to be sufficient to evaluate efficacy (i.e., self-reported/biochemically verified abstinence) in a preliminary behavioral design trial.^{63,64} With respect to percentage reporting self-reported and/or biochemically confirmed abstinence at 3-mo follow up the margin of error (ME) around our observed outcomes depends on the observed proportion with the largest ME occurring when the proportion is 50%. Our sample size is sufficient to provide a ME of 10% (if the proportion is 50%) or less. A study fully powered to determine efficacy will be the focus of an R01 hybrid implementation trial informed by this study.

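### The primary outcome is labelled biochemically verified for everyone, although the plan concedes cotinine cannot accurately verify occasional ENDS users, and baseline use frequency is not used in the analysis

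*Protocol*

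**What the plan says.** **Who enters.** Protocol 6.1 sets the AYA criterion as "14-21 years, current or past 30-day ENDS use, hospitalized, English speaking". Protocol 5.1 and 8.3 and the SAP Design paragraph agree. None gives a minimum number of days of use or a dependence level.

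**Who is tested.** Protocol 27.1: "we will assess salivary cotinine from all participants (not currently on NRT) who report abstinence". Occasional users who report abstinence are therefore tested.

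**What the test can show.** Protocol 5.1 and 27.1 concede: "Although accurate verification will not be possible with participants who are occasional users or those on NRT". SAP Assessments repeats it: "Although accurate verification will not be possible with participants who are occasional users or using NRT". All three places justify the testing partly as a feasibility exercise for later studies in daily users. Occasional use is not defined.

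**How the outcome is labelled.** The hypothesis (Protocol 2.2) is "higher rates of biochemically confirmed self-reported tobacco use abstinence" in the intervention arm. Protocol 27.1, Table 3, has "Self-reported and biochemically verified (salivary cotinine) 30-day tobacco/ENDS use abstinence at 3-mo follow up survey (primary outcome". Neither limits the label to people in whom cotinine is accurate.

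**How it is analysed.** Protocol 27.1 and the SAP specify one binomial model with a logit link comparing arms. Randomisation is stratified by sex and age. Exploratory subgroups are sex and demographic factors. Timeline follow-back is stated only for 3 months. Baseline characteristics are given by example (age of initiation, nicotine dependence).

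**The concern.** Two things follow from open eligibility combined with an unrestricted label.

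First, some participants counted under a verified outcome belong to a group in which, by the plan's own account, the test is not accurate. A reader of the result cannot tell how many.

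Second, someone who uses ENDS about once a month can have 30 use-free days without having quit. Where that background rate exceeds the abstinence rate of regular users, it lifts the proportion in both arms. If these participants also respond less to treatment, the contrast between arms shrinks.

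The SAP says this pilot will inform a fully powered R01 trial. That trial would draw on the control-arm rate and the effect estimate, and both depend on a mix of users that the analysis as written does not describe.

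**Working it through.** **The plan's own figure.** The only precision figure is a margin of error of 10% or less at a proportion of 50%. From 1.96 × √(0.25/n): n = 96 gives 10.0%, n = 144 gives 8.2% and n = 48 gives 14.1%. The stated figure reproduces for the intervention arm and the total, but not for the control arm alone. It does not bear on the mix of users. The plan states no abstinence rate, effect size or share of occasional users, so everything below rests on assumptions.

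**Assumptions.**
- Days of use in 30 days follow a Poisson count with mean λ, so the chance of a use-free window is exp(−λ): 0.368, 0.135 and 0.018 for λ = 1, 2 and 4.
- Regular users reach 10% (control) and 20% (intervention). Odds ratio: (0.20/0.80)/(0.10/0.90) = 2.25.
- Occasional users are 30% of each arm.

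**Case A: no treatment effect in occasional users.** Control = 0.7 × 0.10 + 0.3 × exp(−λ). Intervention = 0.7 × 0.20 + 0.3 × exp(−λ). The occasional share of all abstainers is 0.3 × exp(−λ) divided by the arm's rate.

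| Mean days | Control | Intervention | Odds ratio | Occasional share of abstainers, control / intervention |
|---|---|---|---|---|
| 1 | 18.0% | 25.0% | 1.52 | 61% / 44% |
| 2 | 11.1% | 18.1% | 1.77 | 37% / 22% |
| 4 | 7.5% | 14.5% | 2.09 | 7% / 4% |

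The risk difference is 0.7 × 10 = 7 points in every row, against 10 in regular users. At 4 days the background rate (2%) is below the regular users' 10%, so the control rate is not raised; the remaining dilution comes only from assuming no effect.

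**Case B: occasional users respond with the same odds ratio, λ = 1.** Their treated odds are 2.25 × 0.368/0.632 = 1.31, a rate of 56.7%. Intervention arm: 0.14 + 0.3 × 0.567 = 31.0%. Control stays at 18.0%. The pooled odds ratio is about 2.04, and the risk difference is 13 points.

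**A second set of assumptions.** Take regular users at 10% v 30%, a 40% occasional share, and occasional users at 30% to 50% in both arms. Control is 0.6 × 0.10 + 0.4 × 0.30 = 18% (26% at the upper value). Intervention is 0.6 × 0.30 + 0.4 × 0.30 = 30% (38%). The difference falls from 20 to 12 points, and the odds ratio from 3.86 to between 1.95 and 1.74. The direction is the same.

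**The case against.** The best defence is that the limitation is disclosed three times, with a reason for testing anyway. The trial is a pilot of preliminary efficacy, and broad enrolment is a legitimate choice: the pooled effect is a valid quantity for the population enrolled. That stands, and it is why eligibility need not change. It does not settle how the outcome should be labelled or analysed.

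Several stronger readings are tempting but not supported:

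- *The plan counts every negative test in an occasional user as verified.* This is the natural reading of the label and the single model, but no coding rule is written. The sample-size text speaks of self-reported and/or biochemically confirmed abstinence, so separate reporting remains possible. The gap is the missing rule.
- *The test cannot fail an occasional user.* The documents say only that accurate verification is not possible. A positive result is not excluded.
- *There is no baseline measure of frequency.* The SAP schedules a pre-intervention survey whose items (Table 4 and an Appendix) are not shown. A frequency question may exist. Nicotine dependence is measured and might help identify light users. What can be said is that neither document names frequency in the analysis.
- *Occasional users bias the result towards one arm.* Under randomisation, background abstinence acts on both arms alike.
- *Chance imbalance in the occasional share is a further threat.* At 1 day a month it could move the difference by 1.96 × √(0.3 × 0.7 × (1/96 + 1/48)) × (0.368 − 0.10) = 4 points. That is already part of the roughly 14-point margin on the 18% v 25% difference: 1.96 × √(0.180 × 0.820/48 + 0.250 × 0.750/96).
- *Dilution is large.* The result depends heavily on the assumptions. Most of the fall to 1.52 comes from assuming no effect in occasional users.

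**Conclusion.** The point holds as a mismatch between label and measurement, together with an omission from the analysis. An eligible group is tested and reported under a verified outcome although the plan says it cannot be accurately verified. The analysis as written provides no way to identify or separate that group.

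The consequence is a partly inaccurate label and possible dilution, in neither arm's favour. Its size cannot be established from the documents. Under the stated assumptions at a 30% share, the odds ratio lies between 1.52 and 2.09, against 2.25 in regular users, if occasional users do not respond. It is about 2.04 at 1 day a month if they respond equally.

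For a pilot this is a worthwhile, inexpensive improvement. It is not a flaw that invalidates the comparison. The exemption of participants on NRT from testing is a related but separate matter and is not assessed here.

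**What to change.** Leave eligibility, randomisation and sample size as they are.

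1. **Protocol 5.1, 9.0 and 27.1, and SAP Assessments:** record days of ENDS use and of other tobacco use in the past 30 days at baseline, with the timeline follow-back already planned for 3 months. If the baseline survey already has a suitable item, name it and use that.
2. **SAP, definition:** define occasional use by a prespecified cut-off on baseline days, consistent with the plan's own statement about where cotinine is not accurate. A daily versus non-daily split would not match that statement, since someone using on 25 days a month is non-daily but hardly occasional.
3. **SAP, primary model:** include baseline days of use as a covariate in the logit model.
4. **SAP, reporting:** give self-reported and cotinine-confirmed abstinence separately, overall and by occasional versus regular use. Use the biochemically verified label only outside the occasional group.
5. **SAP, secondary outcome:** add days of use at 3 months, adjusted for baseline days.

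The cost is one short baseline questionnaire (none if the item exists) and a few table rows. The verified result will rest on fewer participants. The subgroup estimates will be imprecise and should be presented as descriptive. Baseline days not recorded at enrolment cannot be recovered later without recall error, so the item should be added or confirmed promptly.
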